**Power and Sample Size.** This study is powered to detect moderate treatment group differences in percent days abstinent (PDA) and percent of days of heavy drinking (PDH), and relationship functioning as measured by the TLFB and DAS-7, respectively at end-of-treatment (weeks 9-12). Assuming 2-sided hypothesis testing and alpha levels of 0.05, we will have 80% power to detect treatment group differences with effect sizes of 0.6 in the presence of 30% attrition (n=70 couples) during the treatment phase. This approach is consistent with treatment group differences in PDA ( $d=0.59$ ) and PDH improvements ( $d=0.79$ ) in a prior ABCT trial (n=102), although we recognize that that trial compared individual therapy vs. ABCT (not ABCT  $\pm$  medication). In that study, PDA increased from  $34.98\% \pm 29.17\%$  to  $80.52\% \pm 27.75\%$  at the end of treatment in the ABCT group, and PDH decreased from  $56.83\% \pm 28.87\%$  to  $10.52\% \pm 22.16\%$  in the ABCT group. Incorporating an arcsine or other appropriate transformation to account for non-normality of these metrics will enable us to discern whether oxytocin enhances end of treatment PDA by an additional absolute 9% or greater (i.e., to 80.5% in the ABCT+ placebo group vs. 89.5% in the ABCT + oxytocin group) and whether oxytocin further decreases PDH by an absolute 6% or greater (i.e., to 10.5%

in the ABCT+ placebo group vs. 4.5% in the ABCT + oxytocin group). Another prior ABCT trial found that DAS-7 scores ( $21.1 \pm 6.7$ ) remain relatively constant throughout treatment. We will have 80% power to detect treatment group differences of 4 units of improvement in DAS-7 scores.

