To test hypotheses 1 and 2, a general linear modeling (GLM) framework will be used, treating end-of-treatment (weeks 9-12) PDA, PDH, and DAS-7 scores as dependent variables (in separate models), and treating treatment group (ABCT + oxytocin vs. ABCT + placebo) as the primary independent variable. Baseline values for PDA, PDH, and DAS-7 will be included as covariates, along with other potentially significant baseline characteristics. Since PDA and PDH may exhibit non-Gaussian distributional forms and/or zero-inflation, alternative modeling strategies (e.g., arcsine or Box-Cox transformations, two-part Hurdle models) may need to be explored. Model fit will be compared by examination of Likelihood Ratio chi-square values. If transformations are necessary, back-transformations will be used in conveying the model results. Similar modeling strategies will be used for secondary exploratory outcomes (described below).

**Hypothesis 3a:** PFC-AMY functional connectivity after treatment will be greater in participants who receive ABCT+ oxytocin compared to those who receive ABCT + placebo.

**Hypothesis 3b:** Baseline PFC-AMY functional connectivity in response to alcohol vs. neutral cues will predict the magnitude of change in alcohol use (PDA and PDH measured by TLFB in the final 3 weeks of treatment).

**Hypothesis 3c:** Baseline PFC-AMY functional connectivity in response to relationship conflict vs. neutral cues will predict amount of change in relationship functioning (IP DAS-7 scores in the final 3 weeks of treatment).

For hypothesis 3, preprocessing and analysis of fMRI data will use FSL v 5.0^148. Preprocessing includes rigid-body head motion correction of EPI images within a run, high-pass temporal filtering (sigma = 150 seconds), geometric distortion correction, slice timing correction, spatial filtering (FWHM = 6 mm) and registration to the MNI standard brain template. 'fsl\_motion\_outliers' will be used to determine head motion outliers which will be used a covariate of no interest in statistical analysis (together with the 6 rigid-body

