**Exploratory Hypothesis 4:** The ABCT + oxytocin group will demonstrate significantly greater improvement in frequency of within-session behaviors (i.e., positive, negative, and alcohol change-talk behaviors measured by the SSCIT-A at sessions 1, 4, 8, and 12) as compared to the ABCT + placebo group.

To test exploratory hypotheses, a nonlinear mixed effects modeling framework will be used, where nonlinearity is likely to arise when participants transition from the treatment to follow-up phase. Separate models will be constructed for IPs and their partners. Time-specific outcome data will serve as dependent variables (in separate models, with treatment group being the primary independent variable of interest. Baseline values for PDA, PDH, DAS-7 and sex will be included as covariates, along with other potentially significant baseline characteristics. Models will include linear (and possibly non-linear) effects for time through the 6-month follow-up, allowing for changes in time effects to occur at end-of-treatment (i.e., using a regression ‘join-point’). Random subject effects will be incorporated to account for the fact that within-subject measurements over time are correlated with each other. Autoregressive covariance structures along with other structures (e.g., compound symmetry, spatial power) will be investigated, with final models based on Akaike Information Criterion. When examining outcomes involving counts (i.e., positive, negative, and alcohol change-talk behaviors), we will assume these variables follow Poisson and/or negative binomial distributions, accompanied by log-link functions within a generalized linear mixed models framework.

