Follow-Up Phase. All participants will be provided with a list of community resources upon study completion. Individuals presenting at any time with serious mental or physical health symptoms including acute alcohol withdrawal will be referred clinically for treatment. All AEs occurring during the follow-up phase will be reported to MUSC IRB and NIAAA. SAEs occurring during the follow-up phase will be reported to MUSC IRB and NIAAA within 48 hours. Any participant demonstrating clinical deterioration will be referred clinically consistent with the procedures outlined in the Human Subjects section. In the event that emergency evaluation or intervention is necessary, the participant will be escorted by a study staff member to the psychiatric walk-in clinic or emergency room. Psychiatric hospitalization is available for emergencies at any point in the study.

Data Management and Analysis. A data analytic plan (including power calculation) is outlined in the Data Analysis section. This study is powered to examine the efficacy of oxytocin versus placebo on the primary outcomes of interest. The main outcome variables include the severity of AUD, relationship functioning, and corticolimbic connectivity determined via neuroimaging procedures. Analyses will be guided by the specific hypotheses of the study and conducted by the study biostatistician, [name]. Post-hoc exploratory analyses will be conducted with two-tailed tests and more conservative statistical procedures which guard against Type I error (e.g., Tukey tests). All primary hypotheses will be tested at level of

significance  $\alpha=0.05$ . We will also estimate the effect sizes of interest and provide 95% confidence intervals. Please see the Statistical Analysis and Power section for more details.

Quality Assurance and Confidentiality. Data quality will be monitored by random inspection of the completed forms by research staff and any irregularities or problems detected will be discussed with the PI. Project therapists will receive standardized training from the PI and Co-Is (Drs. [name], [name], and [name]). [name] developed the ABCT intervention which will be utilized in the proposed study and is currently being tested in several federally-funded trials to examine various adaptations of ABCT. Adherence to the manual will be monitored using videotapes and weekly supervision. If therapy drift is observed the therapists will be re-trained. Booster sessions will be held annually.

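### The plan may replace its default PDA/PDH model, but its only comparison rule, likelihood ratio chi-square values, cannot rank the candidate models

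*Combined protocol and SAP*

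**What the plan says.** Section 11.0, Hypotheses 1 and 2, sets a general linear model for end-of-treatment PDA and PDH, with treatment group as the main predictor and baseline values as covariates. If the outcomes prove non-normal or have too many zeros, "alternative modeling strategies (e.g., arcsine or Box-Cox transformations, two-part Hurdle models) may need to be explored". The list is illustrative, and neither a threshold for leaving the default nor a final model is given. The comparison rule is "Model fit will be compared by examination of Likelihood Ratio chi-square values". No reference model, degrees of freedom, outcome scale or cut-off accompanies it. On reporting: "If transformations are necessary, back-transformations will be used in conveying the model results".

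Section 11.0, Power and Sample Size, is equally open on the transformation ("Incorporating an arcsine or other appropriate transformation to account for non-normality of these metrics") but states its targets as absolute differences: the design "will enable us to discern whether oxytocin enhances end of treatment PDA by an additional absolute 9% or greater", and likewise 6 points for PDH. Section 12.0, Data Management and Analysis, sets alpha at 0.05 and adds "We will also estimate the effect sizes of interest and provide 95% confidence intervals", without naming a scale.

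**The concern.** PDA and PDH are primary outcomes whose distributions are likely to pile up at 0% or 100%, so a move away from the default is a real prospect. If it happens, the plan does not settle which test decides significance. The one rule it offers either has no meaning across the listed models or, on its other natural reading, selects on the strength of the predictors, treatment among them. The reported effect also changes with the model, so a result could be given on a scale that does not match the targets used for power.

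**Working it through.** **Inputs.** Two-sided alpha 0.05 and 70 couples after attrition, hence 35 per arm at 1:1. Section 11.0 gives end-of-treatment PDA 80.52% (SD 27.75) and PDH 10.52% (SD 22.16). Assumptions of this check: beta-binomial outcomes with those moments, the same intraclass correlation in both arms, a 21- or 28-day window and a latent baseline-outcome correlation of 0.3 or 0.5. A censored-normal alternative was also run.

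**1. The plan's targets.** 89.5 - 80.5 = 9.0 points of PDA and 10.5 - 4.5 = 6.0 points of PDH. Both are plain differences in mean percent. Nothing below depends on the plan's 80% power figure.

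**2. Where the rule is valid.** It is valid for nested models on one response scale. Examples are two covariate sets for the same outcome, or lambda = 1 (raw) within a Box-Cox family after an offset, with the Jacobian included.

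**3. Different scales.** For z = g(y), log f(y) = log f(z) + log|g'(y)|. Without the last term, the log-likelihood depends on the units. Recoding percent as a proportion shifts -2logL by 2n ln(100) = 2 x 70 x 4.605 = 644.7. In one simulated data set (n = 70):

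| Outcome coding | -2logL | Treatment p |
|---|---|---|
| Raw PDA, percent | 651.5 | 0.152 |
| Raw PDA, proportion | 6.7 | 0.152 |
| Arcsine square root | 54.4 | 0.094 |

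Arcsine beats raw if PDA is in percent and loses if it is a proportion, although the raw test is identical in both codings.

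**4. Adding the Jacobian.** For arcsine square root, g'(y) = 1/(2 sqrt(y(1-y))), which is infinite at y = 0 and y = 1. Under the assumed distributions, 66-71% of placebo PDH values are 0% and 43-50% of placebo PDA values are 100%. The correction is therefore undefined for much of the sample.

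**5. Hurdle.** Its likelihood combines a probability mass at the boundary with a density elsewhere. It is not nested with the Gaussian models, so the difference has no chi-square reference.

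**6. The other reading: each model against its own null.** This is unaffected by units, but it measures how well treatment and baseline predict the outcome. In the data set above, the chi-squares of the Gaussian candidates ran from 12.1 to 15.1, with treatment p from 0.035 to 0.152. Simulated type I error:

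| Rule | Type I error |
|---|---|
| Fixed raw ANCOVA | 4.3-5.9% |
| Fixed arcsine ANCOVA | 4.5-5.3% |
| Fixed hurdle, joint 2-df test | 5.5-7.6% |
| Largest chi-square against own null | 6.5-8.0% |

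At 28 days and correlation 0.5, a repeat run gave 6.9-7.3% after selection against 4.9-5.2% for raw or arcsine. A further simulation of PDA (20,000 trials, correlation 0.4, a different candidate set) gave 7.4% after selection, 6.2% for the fixed hurdle and 4.7-4.8% for any fixed Gaussian model.

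**7. Back-transformation.** The back-transformed mean is sin²(mean of arcsin sqrt(y)). For 28 days, with the placebo means above and the targets added:

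- PDH: mean arcsine 0.1908 (placebo) and 0.0847 (oxytocin). These return 3.60% and 0.72%, a difference of 2.9 points where the difference in means is 6.
- PDA: 1.2278 and 1.3769. These return 88.69% and 96.29%, a difference of 7.6 points where the difference in means is 9.

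Over the scenarios, the range was 2.7-2.9 for PDH and 7.1-7.6 for PDA. Other runs of the same kind gave up to about 3.0 and 7.8.

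**8. Does the choice matter?** At the plan's targets, raw and arcsine ANCOVA gave different significance verdicts in 6-11% of simulated trials.

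**The case against.** The strongest reply is that this is sensible flexibility. A default is stated, departure is tied to the shape of the data, and a competent analyst would not compare likelihoods across scales without a Jacobian. The back-transformed figure is a legitimate summary of a different quantity. The 6-11% disagreement is how often two sound analyses differ, and naming a model does not abolish it.

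Much of this stands. A reader might infer that the plan has no primary model or no trigger. It has a default and a qualitative trigger; what is missing is the threshold, the destination and a workable rule. A reader might infer that the plan instructs an invalid likelihood comparison. It does not say which comparison is meant, so the units example shows what the rule cannot do, not what the team will do. Nor is the back-transformed effect a wrong estimate; it answers a different question from the power targets.

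Three further inferences are unsupported. The phrase "with final models based on Akaike Information Criterion" closes a sentence on covariance structures in the exploratory mixed models, so it does not show that those models have a selection rule the primary ones lack. How often a hurdle would be selected depends on a selection rule that the plan does not state. The excess type I error cannot be put mainly on the hurdle: in the PDA simulation its own error took the rate from 5% to 6.2%, and selection took it on to 7.4%.

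The reply does not supply a rule that ranks the listed models, and no other section does.

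**Conclusion.** The point holds. The stated rule fails for the set of models it is meant to compare. That conclusion rests on the text and on likelihood theory, not on simulation. The sizes do rest on assumed distributions and correlations: type I error of about 6.5-8% if selection uses each model's chi-square against its own null, with part due to the hurdle's small-sample error and part to selection, against about 5% for a fixed raw or arcsine ANCOVA. Under arcsine back-transformation, 6 points of PDH is reported as about 3 and 9 points of PDA as about 7.5. A reader might infer serious false-positive inflation; the figures show a modest excess, on one reading only. The main harm is an unsettled primary test and effect scale. It should be corrected before unblinding, but it does not undermine the design.

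**What to change.** Before unblinding, amend section 11.0:

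1. Delete the likelihood ratio sentence as the rule for choosing the primary PDA/PDH model.
2. Name one governing model for both outcomes and state that its p-value alone decides significance. Arcsine-square-root ANCOVA with baseline covariates is one example, using the transformation that the power section names. In the simulation, raw ANCOVA had 4-9 points less power at the plan's targets (28.5% against 37.4% for PDH in the 28-day, correlation 0.5 case).
3. Report the adjusted difference in mean PDA and PDH in percentage points with a 95% CI, in place of a back-transformed arcsine difference. If arcsine carries the test, label this interval as estimation. Simulated coverage of the raw ANCOVA interval at the targets was 94.8% (PDH) and 95.6% (PDA).
4. Make the other scale, Box-Cox with its offset stated, and the hurdle with one joint 2-df test sensitivity analyses.

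The cost is wording only. The team gives up choosing a better-fitting model later. An arcsine test can also disagree with the percentage-point interval, in about 6-11% of simulated trials at the targets, which is why the governing test must be stated.

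Two neighbouring matters are separate points. The covariate set is open ("Baseline values for PDA, PDH, and DAS-7 will be included as covariates, along with other potentially significant baseline characteristics", plus the rule of adjusting for variables that differ significantly between arms) and should become a fixed list that includes the TLFB randomization stratum. The end-of-treatment window is three weeks in one place and weeks 9-12 in others, and should be reconciled.

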**Psychosocial Intervention: Alcohol Behavioral Couple Therapy (ABCT).** All participants will receive 12 weekly, 90-minute ABCT therapy sessions delivered by trained Masters or Doctoral-level clinicians consistent with the published manual. The main goal of ABCT is to concurrently reduce AUD symptom severity and improve relationship functioning. Patients receive psychoeducation pertaining to the interconnectedness of AUD and relationship functioning. AUD-focused components of the treatment help patients identify and manage cravings, urges to drink, and thoughts about alcohol use; enhance individual problem solving and decision-making abilities; identify and plan for "high-risk" situations in which vulnerability to relapse is heightened; learn drink refusal skills; and cope with a potential relapse. ABCT also teaches couples to work together to enhance reciprocity and communication skills in the relationship, increase positive rewards of initiating and maintaining drinking reductions and abstinence, and identifying and implementing ways partners can help minimize and manage alcohol use triggers, participate in drink refusal skills, and help prevent relapse.

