**General Procedures.** Following phone screening for preliminary eligibility, participants will complete a baseline assessment. In a private room apart from their partner, participants will be given a full description of the study procedures and asked to read and sign an IRB-approved informed consent form before any study procedures are conducted. In the event of telehealth, separate appointments will be made to meet with each individual partner separately. Consent will be conducted by trained staff (PI, Co-Is, Study Coordinator, or Research Assistant). Ineligible participants will be given treatment referrals as needed. During 1-2 baseline visits, participants will complete a breathalyzer or alcohol saliva test strip (to test current BAC), pregnancy test (for women), ethyl glucuronide (EtG) and phosphatidyl ethanol (PEth) testing, a history and physical (H&P) exam, urine drug screen (UDS), a battery of standardized self-report and interview measures (Table 1).. Note that for telehealth participants, biological specimens will not be collected, however, female participants will be required to take a pregnancy test (provided by study staff) and will be required to verbally confirm a negative result prior to continuing with any procedures. H&P exams will include a physical and neurological examination; orthostatic blood pressure and pulse measurements; and weight and BMI calculation. In the event of telehealth baseline appointment, biological measures will not be collected. Provided full eligibility criteria are met, participants will schedule visits to complete script development needed for the fMRI sessions and a fMRI session (described in the Neuroimaging Procedures section). Participants will then enter the treatment phase, which is a 12-week, double-blind, placebo controlled RCT during which they will receive weekly ABCT therapy sessions in combination with oxytocin or placebo (see Study Interventions and Procedures Section). Intranasal oxytocin has a half-life of approximately 3-4 hours and can be stored, refrigerated, for 2-4 weeks. If a participant misses multiple appointments, a new dose may be dispensed from IDS or Pitt Street Pharmacy. Participants will complete 3- and 6-month follow-up visits. AUD symptoms, relationship functioning, associated problems (e.g., depression), UDS, EtG, and adverse events will be assessed weekly. In addition, participants will be asked to complete a breathalyzer/alcohol saliva test strip while in the same room; after which they will be taken to separate rooms until it is time for therapy. PEth will be examined at baseline, weeks 6 and 12, and at both follow-up assessments. Blood samples will be refrigerated until sent to out for assay. Therapy sessions may be videotaped, with participant consent. In order to explore secondary outcomes such as the effects of treatment on within-session behaviors, we will employ observational coding to assess frequency of positive, negative, and alcohol change talk behaviors (using the SCCIT-A) in ABCT sessions 1, 4, 8, and 12.

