The informed consent document will outline 1) the sponsorship of the study; 2) the nature, purpose and procedures of the research study; 3) the voluntary nature of participation (i.e., participation is not required and can be discontinued at any time; 4) duration of the study; 5) potential risks and discomforts and potential benefits of participating; 6) that all information will be kept confidential subject to the provisions of state and federal law; 7) compensation; 8) alternative treatments; and 9) telehealth procedures and limitations. Participants will be informed that they can discontinue participation in the study at any time and that this decision will not influence the care they receive at any MUSC or VAMC clinic.

**Assessment Procedures.** Some participants may experience distress in response to self-report and interview measures pertaining to AUD symptoms or associated areas of functioning such as relationship problems or depression. Participants may also experience physical or psychological discomfort during the neuroimaging procedures or medication self-administration. However, based on the research team's past experience and available literature the risks involved in the proposed project are minimal and manageable. Nevertheless, we have a specific protocol in place to manage participant distress in the event that it arises. This protocol is discussed in more detail below. Additionally, all participants will receive an evidence-based behavioral intervention (e.g., ABCT) that includes techniques to help reduce distress and anxiety, and improve mood (e.g., communication skills, cognitive restructuring). We will also inform participants during the informed consent process that they may terminate any assessments, study procedures, or therapy sessions at any point. Our past and ongoing research suggests that the measures and methods proposed in this study can be implemented without undue psychological distress or exacerbation of symptoms. This experience includes numerous federally-funded projects with civilians and Veterans with AUD.

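### Exploratory Hypothesis 4 counts in-session behaviours with a log link but no term for minutes coded, so any session coded for less time is read as having fewer behaviours

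*Combined protocol and SAP*

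**What the plan says.** Exploratory Hypothesis 4 in section 11.0 predicts that "The ABCT + oxytocin group will demonstrate significantly greater improvement in frequency of within-session behaviors", coded at sessions 1, 4, 8 and 12. The model text gives time-specific outcomes, "with treatment group being the primary independent variable of interest", baseline covariates, time effects, and this on correlation: "Random subject effects will be incorporated to account for the fact that within-subject measurements over time are correlated with each other". Several covariance structures will be tried, "with final models based on Akaike Information Criterion". For the count outcomes, "we will assume these variables follow Poisson and/or negative binomial distributions, accompanied by log-link functions within a generalized linear mixed models framework".

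On session length, section 2.0 states: "All participants will receive 12 weekly, 90-minute ABCT therapy sessions". The assessment paragraph under Adequacy of Protection against Risks (section 14.0) tells participants that "they may terminate any assessments, study procedures, or therapy sessions at any point". On recording, section 9.0 says only: "Therapy sessions may be videotaped, with participant consent".

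No section names an offset, an exposure variable, the minutes coded per session, or a rule for short sessions. None says whether whole sessions or fixed segments are coded.

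**The concern.** A log-link count model without an exposure term estimates behaviours per session. That equals a rate of behaviour only when every session contributes the same coded time. If one session is coded for 90 minutes and another for 45, the model attributes the difference to behaviour. A random subject intercept does not help, because it is common to all of a person's sessions and cannot follow length differences between them.

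The direction of the error depends on the outcome. A shortened session lowers the count of negative behaviours, which looks like improvement. It also lowers the counts of positive behaviours and change talk, which looks like worsening.

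Two consequences should be kept apart. If shortening is more common in one arm, the group contrast is biased. If it is equally common in both, it adds within-subject variation that a Poisson model with only a subject intercept does not allow for, so the standard error of a group-by-time term is too small.

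**Working it through.** The documents give no power, sample size or error rate for this hypothesis, so there is no stated figure to reproduce.

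**Inputs from the documents.** Planned length is 90 minutes in both arms (section 2.0). Sessions 1, 4, 8 and 12 are coded. Allocation is one-to-one by couple. With 70 couples after 30% attrition (Power and Sample Size), there are 35 per arm. Identified patients and partners are modelled separately, so each couple supplies one person per model. Tests are two-sided at 0.05.

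**Assumptions, not in the documents.** Mean count 20 (or 5) per session; between-subject SD 0.5 on the log scale; session-level negative binomial dispersion 0 to 0.25; 0 to 20% of sessions coded for only 33% to 67% of their length.

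**Step 1: one short session.** With a constant rate, the distortion is minutes/90 − 1. For 60 minutes this is −33%; for 45 minutes it is −50%, a rate ratio of 0.5.

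**Step 2: shortening that differs by arm.** If a fraction p of sessions is coded for half the time, the mean count is multiplied by 1 − 0.5p. The arm with fewer short sessions then has, with no true effect:
- 10% versus 30%: (1 − 0.05)/(1 − 0.15) = 0.95/0.85 = 1.12
- 5% versus 20%: (1 − 0.025)/(1 − 0.10) = 0.975/0.90 = 1.08

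This was checked by simulating null trials (800 per scenario; Monte Carlo standard error about 0.8 points at 5%) and fitting random-intercept models by maximum likelihood. With 5% short on placebo, 20% short on oxytocin and dispersion 0.1, the mean log group estimate without an offset was −0.079, a rate ratio of 0.92. The formula gives 0.90/0.975 = 0.92. Rejection was 10.5% under Poisson and 10.4% under negative binomial. With log(minutes) as an offset, the mean estimate was 0.006 and rejection was 6.1% and 5.9%.

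**Step 3: shortening equal by arm.** The Poisson group main effect without an offset rejected in 4.8% to 6.1% of null trials in every such scenario. The group-by-time test at mean count 20 rejected as follows:

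| Scenario | Poisson, no offset | Poisson, offset | Neg. binomial, no offset | Neg. binomial, offset |
|---|---|---|---|---|
| Equal lengths, dispersion 0 | 3.7% | 3.7% | 3.7% | 3.7% |
| 10% short, dispersion 0 | 15.4% | 5.1% | 7.1% | 4.5% |
| 20% short, dispersion 0 | 21.5% | 4.6% | 5.8% | 4.4% |
| Equal lengths, dispersion 0.1 | 29.6% | 29.6% | 4.9% | 4.9% |
| 10% short, dispersion 0.1 | 33.5% | 28.0% | 4.1% | 5.1% |

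**Step 4: overdispersion alone.** With equal lengths, the Poisson group-by-time test rejected in 19.5%, 29.6% and 49.7% of null trials at dispersion 0.05, 0.1 and 0.25 (mean count 20), and in 26.5% at mean count 5 with dispersion 0.25. The offset changes none of these. A rough formula agrees: the variance-to-mean ratio is φ = 1 + dispersion × mean × 1.13, where 1.13 = exp(0.5²/2) comes from the subject effect. The rejection rate is about 2[1 − Φ(1.96/√φ)]. At mean 20 and dispersion 0.1, φ = 3.26 and the rate is 27.8%, against 29.6% simulated.

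The two problems therefore need separate remedies. The offset corrects unequal coded time, and negative binomial handles overdispersion.

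**The case against.** A reader might infer that the plan's Poisson option by itself carries a false-positive rate well above 5%. The documents do not support that. With equal lengths and no session-level overdispersion the group-by-time rate is 3.7%, and the group main effect stays near 5% when shortening is equal by arm. The model text names treatment group as the term of interest. A group-by-time term is implied by the word improvement in the hypothesis but is not written out.

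The plan also has routes around the inflation. Negative binomial is already an option, and without an offset it held the group-by-time test at 3.7% to 7.1%. An AIC comparison preferred it in at least 99.8% of runs with extra variation, although the plan's AIC sentence concerns covariance structures and does not clearly extend to the distribution. The other covariance structures might absorb some of the excess, depending on implementation. In a separate set of nine Poisson settings where rejection ran from 6% to 34%, estimating a residual scale brought it to 4.5% to 8.0%.

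Nor do the documents show that coded time varies. The right to stop a session is a consent provision, not evidence that sessions are cut short. Optional taping points to missing sessions more than to partial ones. If fixed segments are coded, exposure is constant. Treatment is double-blind with the same manualised sessions in both arms, so unequal shortening is conjecture.

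Finally, an offset changes the estimand to behaviours per coded minute, assumes a roughly constant rate, and conditions on a duration observed after randomisation.

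All of this limits the size of the point, and the last item calls for a sensitivity analysis. It does not remove the gap. If coded time is constant the offset does nothing, and if it differs by arm, neither negative binomial nor the subject intercept corrects the group contrast.

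**Conclusion.** The point holds in conditional form. The count model has no exposure term, so whenever minutes coded differ between sessions, a shorter one is read as fewer behaviours.

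- **Shortening differs by arm:** the group contrast is biased under either distribution. The rate ratio is 1.12 for half-length sessions in 30% versus 10%, and 1.08 for 20% versus 5%, with no true effect. These splits are scenarios, not forecasts.
- **Shortening equal by arm:** only the implied group-by-time test is affected, and only under Poisson with a subject intercept alone. The rate is about 15% to 22% at an assumed mean count of 20 with 10% to 20% of sessions short.
- **Session-level overdispersion:** this is a separate fault of the Poisson option, which an offset does not cure. A reader might infer from the short-session results that the offset is enough; it is enough only when length is the sole source of extra variation.

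This is a cheap improvement to an exploratory analysis. The percent-days-abstinent, heavy-drinking and DAS-7 conclusions are unaffected.

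**What to change.** In the Exploratory Hypothesis 4 text of section 11.0:

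1. State whether whole sessions or fixed segments are coded, and record the minutes coded for sessions 1, 4, 8 and 12.
2. Include log(minutes coded) as an offset in the count models.
3. Make negative binomial the stated model in place of the open choice between it and Poisson.
4. Report the per-session estimate, without the offset, as a sensitivity analysis.

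The cost is one extra variable, which can be read from the recordings being coded, and a line or two in the plan. Nothing changes for participants or for the sample size. The small downside is that the main estimate becomes behaviours per coded minute and assumes a roughly constant rate within a session. The per-session analysis in item 4 shows whether that choice matters.
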